## 4.11 Efficacy Evaluation

### 4.11.1 Analysis and Data Conventions

The statistical hypotheses for testing the activity of RXC004 in module 1 (pancreatic cancer) and module 2 (biliary tract cancer) independently are:

$$H_0: p \leq p_0$$

$$H_1: p \geq p_1$$

Where  $H_0$  is the null hypothesis,  $p$  is the observed response rate,  $p_0$  is the response rate for available treatment options – [REDACTED],  $H_1$  is the alternative hypothesis and  $p_1$  is the target response rate – [REDACTED].

The primary summary measure is the progression free survival rate at 6 months. For module 1 the corresponding  $p_0$  and  $p_1$  are [REDACTED] and [REDACTED]%. For module 2 the corresponding  $p_0$  and  $p_1$  are [REDACTED] and [REDACTED]%.

#### 4.11.1.1 Multi-center Studies

There will not be any adjustment for study centres, subgroup analysis based on study centres are not planned.

#### 4.11.1.2 Adjustments for Covariates

No statistical model will be provided for the analysis of study endpoints.

#### 4.11.1.3 Handling of Dropouts or Missing Data

Missing data will not be imputed.

#### 4.11.1.4 Multiple Comparisons/Multiplicity

Not applicable in this study.

#### 4.11.1.5 Interim Analyses

There is no formal interim analysis planned.

#### 4.11.1.6 Examination of Subgroups

Not applicable in this study.

### 4.11.2 Primary Efficacy Variable(s)

Primary efficacy analyses will be conducted on the FAS. A listing containing information on target, non-target lesions, new lesions, overall response will be provided (ordered by patient and visit).

#### 4.11.2.1 Progression Free Survival

PFS is defined in Section 3.2.1.1.

Kaplan-Meier analyses will be conducted for each module. Survival plots will be produced to present Kaplan-Meier estimated curves. In addition, the following parameters estimated from the Kaplan-Meier curves will be provided for each group:

- Median PFS and corresponding 95% CIs
- PFS rate at 3, 6 and 12 months and corresponding 90% CIs and 95% CI (one month = 30.4375 days).

PFS will be listed for all patients in the FAS.

### 4.11.3 Secondary Efficacy Variables

All secondary efficacy analyses will be conducted on the FAS and, where appropriate, on the evaluable set.

#### 4.11.3.1 Objective Response Rate

Definition of ORR is provided in Section 3.2.1.3. ORR will be based on a individuals BOR using the Investigator RECIST 1.1 assessment.

ORR and associated 90% CIs, calculated using the Clopper Pearson method, will be summarized for FAS and evaluable set.

BOR will be listed for all patients in the FAS.

#### 4.11.3.1 Disease Control Rate

The definition of DCR is provided in Section 3.2.1.4. DCR will be based on a individuals BOR using the Investigator RECIST 1.1 assessment.

DCR and associated 90% CIs, calculated using the Clopper Pearson method, will be summarized for the FAS and evaluable set.

#### 4.11.3.1 Percentage change in sum of target lesions

The % change in sum of target lesions is defined in Section 3.2.1.5 .

Percentage change in tumour size will be derived at each scan assessment by the percentage change from baseline in the sum of diameters of target lesions and will be provided for the FAS. In case some individual lesions are not measured, the whole sum of target lesions will be considered as missing.

% change in sum of target lesions will be always computed considering screening sum of diameters as baseline.

Percentage change in tumour size will be listed per visit for all patients in FAS.

The best percentage change in tumour size will be the patients value representing the largest decrease (or smallest increase) from baseline in tumour size.

A waterfall-plot will be produced to report the best % change in sum of target lesions for each patient (considering the minimum observed value) ordered by largest increase to greatest decrease.

A Spider-plot will be drawn to describe the % change in sum of target lesion. Vertical axis will represent the % change in sum of target lesions (% change in tumour size) while the horizontal axis will represent days from baseline, as follows:

Day (x-axis) = date of RECIST 1.1 assessment – first dose of study treatment (C0D1)

All plots will be provided for the FAS.

#### 4.11.3.2 Overall Survival

OS is defined in Section 3.2.1.8.

Kaplan-Meier analyses will be conducted on the FAS. Survival plots will be produced to present Kaplan-Meier estimated curves.

OS will be listed for all patients in the FAS.

#### 4.11.4 Pharmacokinetics

CCI

### 4.12 Safety Evaluation

Safety summaries and analyses will be based on the FAS as defined in Section 4.5.

#### 4.12.1 Adverse Events

Adverse Events will be collected from time of signature of informed consent form throughout the treatment period and until 30 days after the last dose of RXC004.

SAEs will be recorded from the time of signing of main study informed consent form until the follow-up period is completed: 30 days after the last dose of RXC004 for patients treated with RXC004 monotherapy only) or 90 days after the last dose of Pembrolizumab (for patients treated with RXC004 and Pembrolizumab).

The following variables will be collected for each AE:

- AE (verbatim)
- Start/Stop date
- NCI CTCAE grade at onset and grade changes
- Seriousness
- Investigator causality rating against the Investigational Product(s)
- Action taken with regard to Investigational Product(s)
- Action taken with regards to AE
- Outcome

In addition, the following variables will be collected for SAEs:

- Date AE met criteria for SAE
- Date Investigator became aware of SAE

- Death
- Hospitalisation
- Life threatening
- Congenital anomaly or birth defect
- Disability or permanent damage
- Other medically important serious event
- Date of hospitalisation
- Date of discharge
- Causality assessment in relation to study procedure(s)
- Causality assessment to other medication

Partially complete AE dates will not be imputed in the listings and the available day, month and year components will be used to determine if an adverse event is treatment-emergent taking the first dosing date and last treatment date as references.

More specifically:

- Start date of AE missing: Assumed to be date of first treatment dose.
- Start day and month of AE missing: Assumed to be date of first treatment dose (if same year for both dates), January first otherwise.
- Start day of AE missing: Assumed to be date of first treatment dose (if same month and year for both dates), first day of the month otherwise.
- End date for non-ongoing AE missing: Assumed to date of last treatment dose
- End day and month for non-ongoing AE missing: Assumed to be date of last treatment dose (if same year for both dates), December 31st otherwise.
- End day for non-ongoing AE missing: Assumed to be date of last treatment dose (if same month and year for both dates), last day of the month otherwise.

Treatment-emergent adverse events (TEAEs) with missing relationship to the study drug will be considered as related.

AEs will be coded using the Medical Dictionary for Regulatory Activities (MedDRA), latest version. Grading will be performed using NCI CTCAE version 5.0.

TEAEs are defined as those AEs with an onset after dosing and those pre-existing AEs that worsen after the start of dosing and within 30 days of stopping RXC004.

An overview table of TEAEs will be provided showing the number of patients, the percentage of patients and the number of events for the following categories of events:

- Any TEAE
- Any serious TEAE (STEAE)
- Any treatment related TEAE
- Any serious TEAE related
- Any TEAE leading to permanent discontinuation of RXC004
- Any TEAEs leading to RXC004 reduction
- Any TEAEs leading to RXC004 interruption

For TEAEs, TEAEs considered related, STEAEs, STEAEs considered related, TEAEs leading to study treatment discontinuation, TEAEs leading to RXC004 reduction, TEAEs leading to RXC004 interruption, TEAEs by maximum grade, TEAEs with grade  $\geq 3$ , TEAEs with grade  $\geq 3$  related, death, detailed tables will be created showing the number of patients who experienced at least one TEAE, the corresponding percentage of patients and the number of events by SOC and PT.

For module 1 and 2, AE relatedness corresponds to a relation to RXC004. For Module 3, AE relatedness corresponds to at least one of RXC004/pembrolizumab relation.

For all AE summaries, SOC will be sorted by alphabetical order. PTs, within each SOC, will be sorted by descending order of total frequency. In the event of PTs with equal total frequencies, the relevant PTs will be sorted alphabetically. In addition, a table summarizing TEAEs by decreasing frequency of Preferred Terms will be produced for all TEAEs and TEAEs related.

A table will also be produced showing the details for every patient that die (death date, cause of death etc...).

Listing of all AEs (including non-treatment-emergent events) will be provided. This listing will be presented, ordered by patient. It will include patient identifier, AE (SOC, PT, and verbatim term), date of onset, date of resolution, duration, maximum grade, seriousness, action taken, outcome and causality.

In addition, data related to dysgeusia examination questionnaire will be listed. The data will also be summarized as categorical data providing there are enough data to make it meaningful to do so.

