#### 4.8 Prior and Concomitant Medications

Prior and concomitant medications will be coded using the World Health Organization - Drug Dictionary (WHO-DD) Version March 2023 and will be classified by Anatomical Therapeutic Chemical (ATC) categories. Prior medications will be defined as medications that stopped before the first dose of study drug and will be listed only.

For the purpose of categorizing medications as prior or concomitant, incomplete medication start and stop dates will be imputed as follows:

Missing start dates (where UK, UKN and UNKN indicate unknown or missing day, month, and year respectively):

- UK-MMM-YYYY: Assume 01-MMM-YYYY. If the month and year are the same as the first dose of study drug month and year, then assume the date of first dose of study drug;
- UK-UKN-YYYY:
  - If the year is prior to the year of first dose of study drug, assume 01-JUL-YYYY of the collected year. If the end date is before 01-JUL-YYYY, assume the first day of the year.
  - If the year is the same as the first dose of study drug year, then assume the date of first dose of study drug. If the End Date occurs before the first dose of study drug, then assume the first day of the year.

- If the year is after the first dose of study drug year, then assume the first day of the year.

UK-UKN- UNKN: Assume date of first dose of study drug. In case end date is before first dose of study drug, assume the first day of the year of the CM end date.

Missing stop dates for concomitant medications data will be handled as follows (where UK, UKN and UNKN indicate unknown or missing day, month, and year respectively):

- UK-MMM-YYYY: Assume the last day of the month;
- UK-UKN-YYYY: Assume 31-DEC-YYYY;
- UK-UKN- UNKN: Assume ongoing and leave it missing.

Medications will be categorized as follows:

Medication start and stop dates will be compared to the date of first dose of study medication to allow medications to be classified as either Prior or Concomitant.

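### Incomplete AE start dates are set to the first-dose date without consulting the recorded stop date, so an event known to be over before dosing can be counted as treatment-emergent

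*SAP*

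**What the plan says.** SAP 4.12.1 gives three rules for an incomplete AE start date:

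- Whole date missing: "Start date of AE missing: Assumed to be date of first treatment dose".
- Day and month missing: "Start day and month of AE missing: Assumed to be date of first treatment dose (if same year for both dates), January first otherwise".
- Day missing: "Start day of AE missing: Assumed to be date of first treatment dose (if same month and year for both dates", and the first of the month otherwise.

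Three parallel rules for events that are not ongoing move an incomplete end date towards the last dose, for example "End date for non-ongoing AE missing: Assumed to date of last treatment dose" and "End day for non-ongoing AE missing: Assumed to be date of last treatment dose (if same month and year for both dates". The paragraph that introduces all six rules says that emergence is decided "taking the first dosing date and last treatment date as references". No start rule consults the stop date, and no end rule consults the start date.

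The definition that uses these dates is "TEAEs are defined as those AEs with an onset after dosing and those pre-existing AEs that worsen after the start of dosing", limited to 30 days after stopping RXC004. The same section counts a treatment-emergent event with missing causality as related.

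For medications, SAP 4.8 does use the other date. In the year-only tier, when the year is that of the first dose, it says "If the End Date occurs before the first dose of study drug, then assume the first day of the year". The fully missing tier has a similar check. SAP 4.8 then classes as prior any medication that the dates clearly show to have stopped before dosing.

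**The concern.** Imputing towards the first dose is a sensible cautious choice when the timing is unknown. Here part of the timing is known. A recorded stop before the first dose shows that the event neither began nor worsened after dosing, so it cannot meet the SAP's definition. The rule overrides recorded data.

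Such events can be expected. AEs are collected from consent (Protocol 8.3.1, SAP 4.12.1), screening runs from Day -28 to Day -1 (SAP 4.2.1), a baseline biopsy is mandatory with limited exceptions (Protocol 5.1), and calcium and vitamin D start at consent. Both start and stop dates are collected for each AE, so the information needed for a check is available.

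At stake is the accuracy of the treatment-emergent tables, which are the main safety output, and of the treatment-related tables where causality is missing.

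**Working it through.** The documents state no figure on this point, so there is none to reproduce. The rules were applied exactly as written.

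**Worked example (illustrative dates).** First dose 20 March 2022; AE stop recorded as 12 March 2022.

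| Recorded start | Imputed start | Relative to the recorded stop |
|---|---|---|
| March 2022, day missing | 20 March 2022 | 8 days after |
| 2022 only | 20 March 2022 | 8 days after |
| Fully missing | 20 March 2022 | 8 days after |
| February 2022, day missing | 1 February 2022 | before (rule works) |

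**Same dates under SAP 4.8.** With year only or a fully missing start, the end-date check moves the medication start to 1 January 2022, before the stop. With only the day missing, 4.8 has no such check either, and the start again becomes 20 March. The medication is still classed as prior, because the classification looks at the stop date. AEs have no equivalent override in any tier.

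**Share of date patterns that fail.** Assumptions: every first-dose date in 2022 is taken once, with every pair start ≤ stop inside the 28 days before it, the stop fully known, and an onset on the first-dose date counted as emergent.

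- Pairs per first-dose date: 28 × 29 / 2 = 406. Total: 406 × 365 = 148,190.
- Day missing: the rule fails when the true start shares the first-dose month. For first dose on day d, let k = min(28, d − 1); the failing pairs number k(k + 1)/2. Summed over a month this is 4,872 (31 days), 4,466 (30 days) or 3,654 (28 days). Total: 7 × 4,872 + 4 × 4,466 + 3,654 = 55,622, and 55,622 / 148,190 = 37.5%.
- Day and month missing: the rule fails unless the true start lies in the previous year. Those exceptions number 28 × 406 − 3,654 = 7,714. Failing: 148,190 − 7,714 = 140,476, or 94.8%.
- Fully missing: 100%.

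These are shares of possible date patterns among events with a known pre-dose stop. They are not expected event rates.

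**End dates.** Last dose 10 September 2022; AE start recorded as 20 September 2022. An end given as September 2022, as 2022 only, or fully missing becomes 10 September, 10 days before onset. An end of October 2022 becomes 31 October, which is consistent. Over all pairs in the 30 days after last dose (30 × 31 / 2 × 365 = 169,725), the end precedes the start in 56,354 (33.2%), 160,270 (94.4%) and all of them for the three tiers.

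**The case against.** **The definition refers to onset after dosing, so a first-dose-date onset might not count.** The SAP does not settle this in words. But on the strict reading every AE with a fully missing start would drop out of the treatment-emergent tables. That would defeat the purpose of imputing to that date, and it would sit oddly beside the cautious rule on missing causality. The inclusive reading is the evident intent, though it remains an inference.

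**The introductory paragraph says the known parts of a partial date will be used.** It does, but the specific rules that follow spell out how, and they contain no stop-date check.

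**SAP 4.8 has the same gap.** This is partly right. A reader might infer that 4.8 checks the end date in every tier. It does not do so when only the day is missing. The contrast there rests on the prior/concomitant classification, not on the start-date rule.

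**The effect is small and errs towards caution.** This stands. The error over-counts toxicity, the primary endpoints are untouched, and source data verification (Protocol Appendix A 6) may resolve some blank dates.

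**End dates do not matter.** This largely stands. A reader might infer that impossible end dates damage the safety tables. Emergence depends on onset or worsening, partial dates are not imputed in the listings, and no summary table of AE duration is planned. Duration appears only in a listing, and the SAP does not say whether it is derived from imputed dates.

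**Conclusion.** The gap is real but narrow. It affects only AEs with an incomplete start date and a stop known to precede the first dose, and in the partial-date tiers only when the month or year matches that of the first dose. For those events the rule places a finished pre-dose event in the treatment-emergent tables, given the inclusive reading of the definition.

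The documents do not say how many such events to expect; few are likely. Cohort sizes are redacted. At an assumed 15 to 30 patients, one misplaced patient moves a row by 1/30 = 3.3 to 1/15 = 6.7 percentage points, and only if that patient has no other event in the row. The any-TEAE row would probably not move: Phase 1 incidence was 25 of 25 on monotherapy and 13 of 13 with nivolumab. The effect is on individual SOC, PT or related-event rows.

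A reader might infer that about half of day-missing screening AEs are misclassified. With first doses spread evenly over a 30-day month, an average of (0 + 1 + … + 28 + 28)/30 = 434/30 = 14.5 of the 28 screening days share the first-dose month, or 14.5/28 = 52%. But that counts events whatever their stop date, including those still ongoing at first dose, for which the imputation is a defensible cautious choice. The figure for a known pre-dose stop is 37.5%.

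**What to change.** Add to SAP 4.12.1:

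> If the known (or latest possible) stop date is before first dose, the AE is not treatment-emergent, and the imputed start may not be later than the known stop date.

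Where the stop date is missing, or is partial and could fall on or after first dose, the present rule stays. In the worked example the event remains pre-treatment, and the failure falls to zero by construction.

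As housekeeping, add:

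> An imputed end date may not precede a known start date; otherwise leave the end date missing.

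This second sentence affects only derived end dates and any duration based on them.

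The cost is two sentences and a minor programming change. Data collection, endpoints, design and clinical rules are unaffected.

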6.5 Dose Modification

Dose modifications and stopping criteria for RXC004 are detailed in Section 6.5.1.

For participants in Module 3 (RXC004 in combination with pembrolizumab): Dose modifications and stopping criteria for pembrolizumab are detailed in Appendix L. If either agent is interrupted or discontinued for a related AE, the other agent (pembrolizumab or RXC004) may be continued if the patient is judged (by the investigator) to be receiving clinical benefit.

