8.3.1 Time Period and Frequency for Collecting AE and SAE Information

Adverse Events (and Events of Clinical Interest for pembrolizumab) will be collected from time of signature of main study informed consent form throughout the treatment period and until the 30 days after last dose of RXC004 (for patients treated with RXC004 monotherapy) or 90 days after the last dose of pembrolizumab (for patients treated with RXC004 and pembrolizumab combination therapy), or 30 days following cessation of pembrolizumab treatment if the participant initiates new anticancer therapy, whichever is earlier.

SAEs will be recorded from the time of signing of main study informed consent form.

If the investigator becomes aware of an SAE with a suspected causal relationship to the investigational medicinal product that occurs after the end of the clinical study in a participant treated by him or her, the investigator shall, without undue delay, report the SAE to the sponsor.

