9.4.2.3 Tertiary/Exploratory Endpoint(s)

9.4.3 Safety

9.4.3.1 Adverse Events

Treatment-emergent AEs (TEAEs) are defined as AEs with an onset after dosing and pre-existing AEs that worsen after the start of dosing and within 30 days of stopping RXC004 monotherapy, or 90 days after the last dose of pembrolizumab (for patients in Module 3), or 30 days following cessation of pembrolizumab study treatment if the patient initiates new anticancer therapy, whichever is earlier. For AEs, verbatim terms in the CRF will be mapped to preferred terms and system organ class using the Medical Dictionary for Regulatory activities (version 22.0 or later). CTCAE criteria v5.0 will be used to grade the severity of AEs. The incidence of TEAEs will be summarised by preferred term and system organ class as well as severity. Treatment-related TEAEs will be summarised in the same way. Per-patient incidence of SAEs will also be produced.

By patient, listings of all AEs, deaths, SAEs and TEAEs leading to discontinuation will also be produced.

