12.7 Study Treatment

12.7.1 Study Treatment(s) Administered

Details of RXC004 and denosumab treatment, which are administered in all Modules of the study, can be found in Section 6. Details of pembrolizumab study treatment for Module 3 are provided in Table 17.

Table 17 Study Interventions: Pembrolizumab

Intervention name	Dosage formulation	Unit dose strength	Dosage level	Route of administration	Regimen/ Treatment period	Sourcing
Pembrolizumab (MK-3475)	Solution for infusion	100 mg/vial	400 mg every 6 weeks	IV infusion	Treatment continues until participant meets a criterion for discontinuation (see Section 7)	Provided centrally by Sponsor

IV, intravenous.

RXC004 study treatment is administered in 21-day cycles, in combination with pembrolizumab q6w (i.e., pembrolizumab is dosed on alternate cycles). Pembrolizumab may be administered up to 3 days before or after the scheduled Day 1 of each alternate cycle due to administrative reasons.

RXC004 is to be administered 30-60 minutes after administration of pembrolizumab.

Discontinuation criteria can be found in Section 7.

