#### **4.2.4 End of Study (EoS)**

A patient is considered to have completed the study if he/she has completed all phases of the study (including the last visit and the last scheduled assessment shown in the SoA) or withdraws consent whichever occurs first.

The EoS is defined as the date of the last visit of the last participant in the study or the last scheduled assessment shown in the SoA for the last participant in the study before the data cut off (DCO). The study data is planned to be analysed and reported based on all patient data at the primary completion data cut-off date (approximately 24 weeks after cycle 1 day 1 for the last patient in), or at the End of Study, whichever comes first.

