#### 4.16 Changes in the Conduct of the Study or Planned Analysis

After an ongoing review of the available data the following changes to the final outputs were made compared to the protocol:

- Medical History will not be summarized but will be listed.
- CCI
- Overall Survival will not be summarized but will be listed.

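### For Module 3, the SAP ends the TEAE window 30 days after RXC004, whereas the protocol ends it on a pembrolizumab-based date

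*SAP*

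**What the plan says.** **TEAE window.** SAP 4.12.1 gives one definition with no module qualifier: "AEs with an onset after dosing and those pre-existing AEs that worsen after the start of dosing and within 30 days of stopping RXC004". Protocol 9.4.3.1 separates the treatments: "within 30 days of stopping RXC004 monotherapy, or 90 days after the last dose of pembrolizumab (for patients in Module 3"). It then adds an alternative Module 3 end, 30 days after pembrolizumab cessation when the patient starts new anticancer therapy, and takes the earlier date.

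**AE collection.** SAP 4.12.1 says AEs are collected "throughout the treatment period and until 30 days after the last dose of RXC004". Its next sentence gives combination patients a longer period, 90 days after pembrolizumab, but for SAEs only. Protocol 8.3.1 sets the longer period for all AEs: "or 90 days after the last dose of pembrolizumab (for patients treated with RXC004 and pembrolizumab combination therapy"), with the same new-therapy alternative.

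**Declared changes.** SAP 4.16 states that "the following changes to the final outputs were made compared to the protocol" and lists three items. The two legible ones concern medical history and overall survival. The third is blacked out in the public copy.

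**Dosing.** Under protocol 12.7.1, RXC004 is given "in combination with pembrolizumab q6w (i.e., pembrolizumab is dosed on alternate cycles"). Protocol 6.5 lets the drugs stop at different times: "If either agent is interrupted or discontinued for a related AE, the other agent (pembrolizumab or RXC004) may be continued" if the investigator judges that the patient benefits.

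**The concern.** A programmer following the SAP would build the Module 3 TEAE tables (all, related, serious, grade 3 or higher) on a window that ignores pembrolizumab dosing. The same SAP section counts a Module 3 event as related if it is related to either drug, and protocol Appendix L warns that immune-related events may appear months after pembrolizumab ends. The SAP would also be at odds with itself, because some SAEs that it says are recorded would fall outside its own serious-TEAE tables.

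Protocol version does not explain the difference. SAP section 1 names protocol Version 6 as its base, and protocol Appendix M shows that Module 3 came in with Version 5.0. The SAP also handles Module 3 explicitly elsewhere, for example in the dose-intensity formulas of SAP 4.10. Protocol 12.3.1 says RXC004 had not been given with pembrolizumab before, so these tables are a main safety summary of a new combination.

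**Working it through.** The plan states no figure to reproduce. The check is day arithmetic.

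**Inputs.** R is the day of the last RXC004 dose and P the day of the last pembrolizumab infusion. The SAP end is R + 30 (SAP 4.12.1). The protocol end is P + 90 without new therapy, or cessation + 30 with it if that is earlier (protocol 9.4.3.1). The dosing interval is 6 weeks, or 42 days (protocol 12.7.1). The documents do not report actual stopping gaps, so the values of R − P are illustrative.

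**Step 1: no new anticancer therapy, 30-day limit read as covering new-onset and worsening events.** Protocol end minus SAP end = (P + 90) − (R + 30) = 60 − (R − P).

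| R − P (days) | Difference | SAP window is |
|---|---|---|
| −42 (RXC004 stops first) | 60 + 42 = 102 | 102 days shorter |
| 0 | 60 − 0 = 60 | 60 days shorter |
| 21 | 60 − 21 = 39 | 39 days shorter |
| 42 | 60 − 42 = 18 | 18 days shorter |
| 60 | 60 − 60 = 0 | equal |
| 84 | 60 − 84 = −24 | 24 days longer |

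At R − P = −42 the SAP window closes at R + 30 = P − 12, which is 12 days before the last infusion. At R − P = 0, an SAE starting on days 31 to 90 lies inside the SAP's SAE recording period but outside its TEAE window.

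**Step 2: new anticancer therapy.** Protocol 9.4.3.1 counts 90 days from the last dose but 30 days from cessation, and does not define cessation. Two readings are possible.

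- Cessation is the last infusion. The difference is (P + 30) − (R + 30) = −(R − P): 0, −21 and −42 at R − P = 0, 21 and 42. The SAP window is 0 to 42 days longer.
- Cessation is P + 42, the convention that SAP 4.10 uses for pembrolizumab duration. The protocol end is P + 72, earlier than P + 90. The difference is 42 − (R − P): 42, 21 and 0. The SAP window is 42 to 0 days shorter.

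**Step 3: RXC004 outlasts pembrolizumab.** Read literally, the protocol window can close before the last RXC004 dose. Without new therapy this happens once R − P exceeds 90; at 105, P + 90 = R − 15. With new therapy and cessation at the last infusion, it happens once R − P exceeds 30; at 42, P + 30 = R − 12.

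**Step 4: the other reading of the 30-day limit.** The SAP sentence can be read as limiting only worsening pre-existing events. Protocol 9.4.3.1 has the same construction. Read narrowly in both documents, new-onset events have no stated end in either, and the differences above apply only to worsening events.

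**The case against.** The strongest reply has four parts.

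1. **The tables are descriptive and nothing is lost.** The SAP's listing of all AEs includes those that are not treatment-emergent. Site collection is governed by protocol 8.3.1 and by the 90-day follow-up visit in the Module 3 schedule. This stands: the SAP's collection sentence is mainly an editorial conflict. It does not repair the TEAE tables.
2. **The day counts depend on reading the 30-day limit as covering new-onset events**, and the SAP inherited that ambiguity from the protocol. This stands as a condition on the figures. Even on the narrow reading, worsening events in Module 3 get different end dates in the two documents.
3. **The change may have been declared.** With one SAP 4.16 item blacked out, that cannot be excluded.
4. **Protocol 6.6 uses 30 (+3) days for Module 3 AEs.** It does, but only for continued access after data cut-off, and counting from the last dose of either drug. It does not support an RXC004-only window.

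A reader might infer that the SAP necessarily understates Module 3 toxicity. The documents do not support that: with new therapy, or when RXC004 continues more than 60 days past the last infusion, the SAP window can be the longer one, and no rate of post-study therapy is given. A reader might also infer that the data cut-off truncates the protocol window. That is a separate matter. SAP 4.2.4 sets the cut-off at "approximately 24 weeks after cycle 1 day 1 for the last patient in", while protocol 9.4.1 ties the Module 3 cut-off to 90 days after the last subject's final pembrolizumab dose. Those two statements need their own reconciliation.

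**Conclusion.** The mismatch is real, and no legible text resolves it: followed as written, the SAP gives Module 3 TEAE tables that do not use the protocol's definition. It should be fixed.

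Without new therapy, and with the limit covering new-onset events, the SAP window is shorter for any RXC004 stop earlier than 60 days after the last infusion. When pembrolizumab continues alone, the SAP window can close during study treatment. On the same reading, serious events recorded late can drop out of the serious-TEAE tables. With new therapy, even the sign of the difference turns on the undefined term cessation. The net effect on reported incidence cannot be stated. The Module 3 primary endpoint is not touched.

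**What to change.** - In SAP 4.12.1, give Module 3 its own TEAE window, taken from protocol 9.4.3.1 and stated to apply to both new-onset and worsening events.
- Define pembrolizumab cessation, and state which end date applies when RXC004 outlasts pembrolizumab. Declare any addition to the protocol definition in SAP 4.16.
- Align the SAP's sentence on collecting non-serious AEs with protocol 8.3.1.
- If the RXC004-only window is intended for Module 3, declare that departure in SAP 4.16 instead.

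The cost is SAP wording and one derivation flag, and collection is already planned under protocol 8.3.1. The exception is the rule for RXC004 outlasting pembrolizumab. It goes beyond protocol 9.4.3.1 and could reach past the literal collection end in 8.3.1, so it may also need a protocol clarification. The downside is that reported Module 3 incidences may change, in either direction.
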